- o. Endometrial biopsy will be performed at screening and at week 52/EOT and in the case of uterine bleeding during treatment. Subject may schedule the endometrial biopsy on a separate day, within the screening period. Subjects that require a retest biopsy due to insufficient or unevaluable result will have an extended screening period and will be allowed an additional 15 days of screening (i.e., days -50 to -1). Screening biopsy results are valid for study entry for up to 3 months from date of procedure for applicable subjects. Subjects who screen failed due to the COVID-19 pandemic study suspension and have a documented evaluable endometrial biopsy from the original screening period do not have to undergo a repeat biopsy should they decide to rescreen. If a subject discontinues from the study, an endometrial biopsy will be performed at the discontinuation visit along with all other EOT procedures. If a subject discontinues from the study, an endometrial biopsy will be performed at the discontinuation visit along with all other EOT procedures.
- p. For HBsAG, anti-HCV antibodies, anti-HBs antibodies, anti-HBc antibodies and anti-HIV antibodies.
- q. Pharmacodynamic samples will be taken predose at day 1 (visit 2), week 12 (visit 5), week 16 (visit 6), week 24 (visit 8) and EOT/ED week 52 (visit 15), as well as predose and 3 hours postdose at week 4 (visit 3). The week 4 (visit 3) 3 hours postdose pharmacodynamic sample may be shifted to a later date (prior to week 12) in case the subject cannot accommodate the sampling schedule at that visit. The pharmacodynamic sample should be taken at the same time as the 3-hour postdose pharmacokinetic sample. A pharmacodynamic sample will be taken at the follow-up visit (week 55 [visit 16]) as well. Markers include LH, FSH, E2, SHBG, androstenedione, dehydroepiandrosterone, estrone and testosterone.
- r. Pharmacokinetic samples to be taken at predose (1 hour), 1 h (\pm 30 min) post dose and 3 h (\pm 30 min) postdose week 4 (visit 3) and week 16 (visit 6), as well as predose, week 12 (visit 5), week 24 (visit 8) and EOT/ED week 52 (visit 15). The indicated time windows for week 4 (visit 3) pharmacokinetic sampling will allow for flexibility. If this visit is missed, the samples can be taken at the next visit (prior to week 12). A pre-dose sample will be collected for any subject with a signal of elevated transaminases ($> 3 \times$ ULN) when she returns for a repeat blood draw.

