6.7 Analysis of Pharmacodynamics

Serum concentrations of sex hormones (LH, FSH, E2, Testosterone Total/Free, Androstenedione, DHEA, Estrone) and SHBG will be summarized using descriptive statistics (number of subjects, mean, SD, median, minimum and maximum) for each analysis and for change from the baseline to each postdose visit, if the data is available.

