| Target day | Analysis window | Analysis visit |
|------------|---|----------------|
| D1 | last non-missing value on or prior to day 1 | Baseline |
| D29 | FD22 to FD36 | Week 4 |
| D85 | FD72 to FD 92 | Week 12 |
| D113 | FD106 to FD120 | Week 16 |
| D141 | FD134 to FD148 | Week 20 |
| D169 | FD162 to FD176 | Week 24 |
| D197 | FD190 to FD204 | Week 28 |
| D225 | FD218 to FD232 | Week 32 |
| D253 | FD246 to FD 260 | Week 36 |
| D281 | FD274 to FD288 | Week 40 |
| D309 | FD302 to FD316 | Week 44 |
| D337 | FD330 to FD344 | Week 48 |
| D365 | FD358 to FD372 | Week 52 |

The VMS efficacy windows are smaller because they are calculated from daily data and are not dependent on the scheduling of visits. The non-VMS efficacy endpoint are not collected during the follow-up period.

If more than one observation exists within the analysis window, the observation closest to the scheduled visit day will be selected for that visit. If there are two observations that have the same distance from the scheduled day, the value that is before the scheduled day will be selected in the analysis. If more than one observation is made on the same day, an average value if continuous, or the worst value if categorical, will be included in the analysis.

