6.10.1.2 Safety Analysis Windows

Except for adverse events, for the analysis window, the last day is always 1 day after the last day of exposure to overall study treatment.

The end of overall treatment is defined as the last day of treatment (e.g., discontinued study or entered follow-up period) +1 and the follow-up period for analysis windows begins at last overall treatment + 2 days and onward (Follow-up Study Day 2).

| Analysis | Scheduled | Analysis Windows (Fezolinetant day) | | | |
|-----------|--------------------|-------------------------------------|----------------------|---------------------|-----------------|
| Visits | Day in Protocol | a) | b) | c) | d) |
| Baseline | Day 1 | Last non-missin | ng value on or prior | to fezolinetant day | y 1 (inclusive) |
| Week 2 | Day 15 | 2 to 22 | | | |
| Week 4 | Day 29 | 23 to 43 | 2 to 43 | 2 to 57 | |
| Week 8 | Day 57 | 44 to 71 | 44 to 71 | | |
| Week 12* | Day 85 | 72 to 92 | 72 to 99 | 58 to 99 | 2 to 127 |
| Week 14 | D99 | 93 to 106 | | | |
| Week 16 | D113 | 100 to 127 | 100 to 127 | 100 to 127 | |
| Week 20 | D141 | 128 to 155 | 128 to 155 | 128 to 155 | |
| Week 24 | D169 | 156 to 183 | 156 to 183 | 156 to 183 | 128 to 267 |
| Week 28 | D197 | 184 to 211 | 184 to 211 | 184 to 211 | |
| Week 32 | D225 | 212 to 239 | 212 to 239 | 212 to 239 | |
| Week 36 | D253 | 240 to 267 | 240 to 267 | 240 to 267 | |
| Week 40 | D281 | 268 to 295 | 268 to 295 | 268 to 295 | |
| Week 44 | D309 | 296 to 323 | 296 to 323 | 296 to 323 | |
| Week 48 | D337 | 324 to 351 | 324 to 351 | 324 to 351 | |
| Week 52** | D365 | 352 to 376 | 352 to 376 | 352 to 376 | 268 to 376 |
| Week 55 | D386 | Last non-missin | ng follow-up day | | |

The data summary by visits will be done following the analysis windows specified in the table below:

a) Apply to liver biochemistry and INR testing

- b) Apply to complete Clinical laboratory and urinalysis, Vital signs
- c) Apply to Blood PD/PK sample, including hormones (PD only at Week 55)
- d) C-SSRS

*The analysis window for the Week 12 ECG assessment (Target Day 85) is FDay 2 through FDay 99

**The analysis window for the Week 52 ECG is last non-missing day from FDay 100 to FUD1; The analysis window for the Week 52 bone marker is FDay 2 to FUD1; The analysis window for the Week 52 TVU and biopsy assessments is FDay 2 until last treatment + 30 days.

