If more than one observation exists within the analysis window, the same rules will be followed as described above for efficacy analysis visit windows, except that if there are two observations that have the same distance from the scheduled day, the value that is after the scheduled day will be selected in the analysis.

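### Followed as written, the 52-week SAP blends the Week 4 predose and 3-hour postdose hormone samples, so its Week 4 row mixes sampling times and does not match between continuing and switched groups

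*SAP*

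**What the plan says.** The hormone schedule is in protocol Table 1, footnote q, and in section 5.3.4. Footnote q begins "Pharmacodynamic samples will be taken predose at day 1 (visit 2), week 12 (visit 5), week 16 (visit 6") and continues with Weeks 24 and 52. Week 4 is the only visit with a second sample: "as well as predose and 3 hours postdose at week 4 (visit 3"). That postdose sample "may be shifted to a later date (prior to week 12) in case the subject cannot accommodate the sampling schedule at that visit".

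Protocol section 7.7 asks for hormone summaries by visit and by time point, and 12-week SAP section 6.7 repeats this. Section 6.7 of the 52-week SAP instead summarises hormones "for each analysis and for change from the baseline to each postdose visit, if the data is available", with no time-point level. Its section 6.4.2 reports one median change per analysis visit.

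In 52-week SAP section 6.10.1.2, window column c is defined as "Apply to Blood PD/PK sample, including hormones (PD only at Week 55"). The Week 4 line is "Week 4 | Day 29 | 23 to 43 | 2 to 43 | 2 to 57". Column c therefore runs from fezolinetant day (FD) 2 to 57 for Week 4, and the next line gives FD58 to FD99 for Week 12. Where a window holds several observations, "the same rules will be followed as described above for efficacy analysis visit windows", except that ties go to the value after the scheduled day. The rules carried over from section 6.10.1.1 are to take the observation closest to the scheduled day and, for one day, "If more than one observation is made on the same day, an average value if continuous, or the worst value if categorical".

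**The concern.** A predose and a 3-hour postdose sample are two planned measurements at different points of the dosing interval. The same-day rule treats them as duplicates of one measurement. If it is applied to hormones, the Week 4 value is neither a predose nor a postdose value for women sampled on one day, and it cannot be compared with the other on-treatment visits, which are all predose.

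The 52-week table also sets four groups side by side on a clock that starts at the first fezolinetant dose. If two of them carry blended values at Week 4 and two carry predose values, a reader could take a difference in sampling time for a difference between women who continued and women who switched.

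**Working it through.** The documents state no sample size, power or effect for the hormone endpoint, so there is no figure to reproduce. The check is to apply the written rules.

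**Inputs.** Week 4 target Day 29, window FD2 to FD57. Week 12 target Day 85, window FD58 to FD99. Visits may be 3 days early or late (protocol Table 1). FD = assessment date − first fezolinetant dose date + 1 (52-week SAP 6.10.1). Half-life 4 to 6 h (protocol 1.3.2).

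**1. Same-day pair.** Both samples have the same FD, so the reported Week 4 value is (predose + 3 h postdose) / 2.

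**2. Shifted postdose sample, visits on target (Days 29 and 85).** Possible shift days are FD30 to FD84, which is 55 days.
- FD30 to FD57 (28 days): inside the Week 4 window, but the Day 29 predose sample is closer, so the postdose sample is dropped.
- FD58 to FD84 (27 days): inside the Week 12 window, but the Day 85 predose sample is closer, so it is dropped.

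It is left out of the summary on all 55 days.

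**3. Shifted postdose sample, Week 4 visit early.** The postdose value becomes the Week 4 value when its distance from Day 29 is no larger than that of the predose sample (ties go to the later value):
- predose Day 26: postdose on Days 27 to 32
- predose Day 27: postdose on Days 28 to 31
- predose Day 28: postdose on Days 29 to 30

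**4. Relabelling as Week 12.** From FD58 the postdose sample is reported as Week 12 if no Week 12 predose sample is closer to Day 85. This happens if that sample is missing. It also happens if the visit is late and the postdose sample is closer: with a Week 12 visit on Day 87 (2 days off), a postdose sample on Day 84 (1 day off) is chosen.

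**5. Switched groups.** With the first extension dose on Day 85, the protocol Week 16 draw on Day 113 has FD = 113 − 85 + 1 = 29, which is Week 4. For extension starts on Days 82 to 88 it falls on FD32 to FD26, still in the Week 4 window. That draw is predose only. The protocol Week 24 and Week 52 draws fall on FD85 and FD281 (Weeks 12 and 40). Continuing women are sampled at Weeks 4, 12, 16, 24 and 52. By schedule, then, Weeks 4 and 12 are the only on-treatment hormone rows shared by all four groups, and Week 4 is the one affected by averaging.

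**6. Exposure at the two samples.** From 3 h to 24 h is 21 h. Assuming simple exponential decline, concentration at 24 h relative to 3 h is 2^(−21/half-life): 2.6% for 4 h, 5.4% for 5 h and 8.8% for 6 h. This is drug concentration, not hormone response.

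**7. Conditional size.** Let x be the difference between 3 h and predose hormone values, and f the fraction of women whose postdose sample was shifted and dropped. The continuing groups' mean is then offset from a predose-only mean by (1 − f) × x / 2. Neither x nor f is in the documents. If x is 10, 20 or 40 points, the offset is 5, 10 or 20 points with f = 0, and 2.5, 5 or 10 points with f = 0.5.

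**The case against.** The strongest reply is that this is a drafting slip. The 52-week SAP says that it elaborates the protocol, and protocol 7.7 has the time-point level. Its change table (version 1 to version 2 only) lists no change to hormone time points, and the sentence in 6.7 reads as if a word was lost. The same-day rule looks like a generic duplicate rule. Column c also covers pharmacokinetic samples, which are only listed, so being in that column need not imply pooling. All this makes an oversight at least as likely as a decision to average. It does not remove the problem: nothing in the 52-week SAP separates the two samples, and the instruction it gives is to average.

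A reader might infer that the 3-hour hormone result is lost from the trial. The documents do not support that. The randomised Week 4 data, with placebo control, are covered by the 12-week SAP, whose section 6.7 keeps the time point. The protocol synopsis also has individual hormone concentrations listed. A sample that is dropped here is missing from a summary row, not from the data.

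A reader might also infer from the half-life that averaging halves a hormone effect that is almost absent at trough. That would need each hormone to follow drug concentration. The documents give no within-day hormone profile in menopausal women, and protocol section 1.3.1 reports an effect on LH but none on FSH in monkeys. One tracking assumption cannot serve for the whole panel.

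**Conclusion.** The point holds for the 52-week SAP. Followed as written, it averages same-day Week 4 pairs, usually drops a shifted postdose sample from the summary, and in limited circumstances lets it stand as the Week 4 or Week 12 value. The Week 4 row is a mixture for 30=>30 and 45=>45, dominated by averages where both samples were taken on one day. It is purely predose for placebo=>30 and placebo=>45.

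It would be too strong to say that every continuing woman contributes a predose/postdose average, because shifted samples mostly leave a pure predose value. Relabelling as Week 12 is an edge case of unknown frequency. The 12-week SAP shares the duplicate rule but keeps the time point in 6.7, so it needs clarification only.

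The consequence is limited. The endpoint is exploratory, the 52-week analysis makes no statistical comparisons, and the switched and continuing groups already use different hormone baselines by design. No co-primary or key secondary result depends on it. The size of any hormone distortion is unknown.

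**What to change.** In 52-week SAP section 6.10.1.2, state that the window and duplicate rules apply to pharmacodynamic samples within nominal time point, so that by-visit hormone rows use predose samples only. Report the Week 4 3-hour postdose sample as its own row for the two continuing groups. State that a shifted sample keeps that nominal label whatever its date; without this, a sample taken on FD58 to FD84 would still fall in the Week 12 window. In section 6.7, restore the summary by visit and time point, in line with protocol 7.7.

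The Week 4 predose row would then be available and alike in all four groups, and no value would be averaged across time points.

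In the 12-week SAP, one sentence in section 6.10.1.2 saying that the same-day and window rules apply within time point is enough.

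The cost is a few sentences and one extra table row. No new data are needed.

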6.10.2 Imputation Rules for Incomplete Dates

In case of missing partial start and stop dates for concomitant medications or targeted medical history, the following rules will be used:

If the start date is missing or partial:

• if the month is missing, use January

- if the day is missing, use the first day of the month under consideration
- if the year is missing, use year of the informed consent date
- if the entire date is missing, use informed consent date

If the stop date is missing or partial:

- if the month is missing, use December
- if the day is missing, use the last day of the month under consideration
- if the year or the entire date is missing, set the stop date to December 31st, 2099

If the imputed start date is after the stop date, then the imputed start date will be 1 day prior to the stop date.

For AEs, a missing or incomplete onset date will be imputed according to the following conventions.

If an onset date is missing, the imputed onset date will be the date of first dose of study drug.

If only the year is known for the AE onset date, the imputed onset date will be the latest of the following non-missing dates:

- Date of first dose of study drug
- January 1 of the year of AE onset date

If only the month and year is known for the onset date, set the surrogate onset date to the first day of that month and then apply the following rules.

- If the month and year of the onset date is prior to the month and year of the first dose of study drug, then the surrogate onset date will be the imputed onset date.
- If the month and year of the onset date is on or after the month and year of the first dose of study drug, then the imputed onset date will be the latest of the following non-missing dates:
 - Date of first dose of study drug
 - Surrogate onset date

If the imputed onset date is after the adverse event end date, the imputed onset date will be the same as the adverse event end date.

7 **REVISION AND RATIONALE**

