7.9 Additional Conventions

Missing data may be the result of missing week 4/week 12 frequency/severity of VMS measurements or the result of patients discontinuing treatment prior to week 4/week 12. Missing at random will be assumed. Details will be provided in the SAP.

The start and stop dates of AEs and concomitant medication will be imputed. The imputed dates will be used to allocate the concomitant medication and AEs to a treatment group, in addition to determining whether an AE is/is not treatment emergent. Listings of the AEs and concomitant medications will present the actual partial dates; imputed dates will not be shown. See the SAP for details of the definition for analysis windows to be used for analyses by visit.

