5 ENDPOINTS

The calculation of efficacy baseline for VMS frequency and severity is described in the 12-week analysis SAP, and will be calculated based on the number of moderate to severe hot flashes in the 10 days immediately prior to randomization.

For general efficacy endpoints collected at visits, the last non-missing assessment on or prior to the first dose of study treatment (investigational product or placebo) is the baseline.

For all general safety endpoints, in contrast, the baseline value will be the last non-missing value taken on or prior to first dose of fezolinetant.

Note that the baseline calculations differ between efficacy and safety analyses. The efficacy endpoints are subjective and there is expected to be a non-ignorable placebo effect, so the entire double-blind portion of the study is considered post-baseline for all subjects. For safety endpoints, any changes while on placebo during the double-blind portion of the study are expected to be within-subject variation and changes from baseline will be assessed beginning with exposure to fezolinetant.

The table below provides additional details regarding the baselines for specific endpoints. The terms R_{BL} and $WK12_{BL}$ indicate where the baseline is established, where R_{BL} is initial randomization and $WK12_{BL}$ is the start of the extension period at Week 12.

| Endpoint | Baseline | | |
|--|-----------------|-----------------|--|
| - | fezolinetant / | placebo / | |
| | fezolinetant | fezolinetant | |
| General efficacy | R _{BL} | R _{BL} | |
| General safety and TVU | R _{BL} | $WK12_{BL}$ | |
| Hormones | R _{BL} | $WK12_{BL}$ | |
| Demographics | R _{BL} | R_{BL} | |
| Medical history | R _{BL} | R _{BL} | |
| Prior medications | R _{BL} | $WK12_{BL}$ | |
| Concomitant medications | R _{BL} | $WK12_{BL}$ | |
| Study drug exposure and compliance | R _{BL} | $WK12_{BL}$ | |
| TEAE | R _{BL} | $WK12_{BL}$ | |
| Clinical lab summary shifts and liver safety assessments | R _{BL} | $WK12_{BL}$ | |
| Protocol deviations | R _{BL} | R _{BL} | |
| Biopsy (Listing only) | R _{BL} | R _{BL} | |

The 12-week double-blind placebo period will be completely described as part of the treatment comparisons within the 12-week double-blind analyses. As a result, all endpoints in the 52-week analysis are from the first dose of fezolinetant and onward (see Section 6.10 for additional details).

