6.5.1 Adverse Events

TEAE is defined as an AE observed after starting administration of fezolinetant and up to 21 days after the last dose of study drug.

A study drug-related TEAE is defined as any TEAE with a causal relationship of YES by the investigator.

The sponsor has a list of events that they classify as "always serious" events. If an AE is reported that is considered by the sponsor to be an SAE per this classification as "always serious", the AE will be treated as an SAE in tables and listings, and flagged as 'always serious' in AE listings.

An overview table will include the following

- Number of TEAEs,
- Number and percentage of subjects with TEAEs,
- Number of drug related TEAEs,
- Number and percentage of subjects with drug related TEAEs,
- Number of serious TEAEs,
- Number and percentage of subjects with serious TEAEs,
- Number of serious drug related TEAEs,
- Number and percentage of subjects with serious drug related TEAEs,
- Number of TEAEs leading to permanent discontinuation of study drug,
- Number and percentage of subjects with TEAEs leading to permanent discontinuation of study drug, and
- Number of deaths.

The number and percentage of subjects with TEAEs in the following AE categories will be summarized for each treatment group by system organ class (SOC), high level term (HLT) and preferred term (PT):

- TEAEs
- drug related TEAEs.

The number and percentage of subjects with TEAEs in the following AE categories will be summarized by SOC and PT:

- serious TEAEs,
- drug related serious TEAEs,
- TEAEs leading to permanent discontinuation of study drug,
- drug related TEAEs leading to permanent discontinuation of study drug,
- TEAEs that equal to or exceed a threshold of 5.0% in any treatment group (threshold is based on PT).
- TEAEs excluding serious adverse events that equal to or exceed a threshold of 5.0% in any treatment group.

The number and percentage of subjects with TEAEs, as classified by PT only, will be summarized for each treatment group.

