6.5.5 Other Safety-Related Assessments

C-SSRS results will be summarized by treatment group and analysis visit based on SAF_F.

Ultrasound results (endometrial thickness) and bone marker results will be summarized for the SAF_F population using mean, standard deviation, minimum, maximum and median by treatment group and visit. The within-subject change will be calculated per visit as the post-baseline measurement minus the baseline measurement and summarized by treatment group and visit. The listing will be based on the complete SAF population, including all placebo data and subjects randomized to placebo who never received fezolinetant, because these data were not included in the double-blind 12-week analysis.

Baseline biopsy will be defined as the non-missing value on or prior to first dose of study drug. Biopsy results will be listed based on the complete SAF population, including all placebo data and subjects randomized to placebo who never received fezolinetant, because biopsy data was not included in the double-blind 12-week analysis. Post-baseline biopsy results for subjects originally randomized to placebo will still be listed.

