6.10.1 Analysis Windows

Study Day for analysis windows during the double-blind treatment phase will be calculated as date of visit/assessment – first dose date +1.

Study Day during the extension phase will be calculated as date of visit/assessment – first dose date of the extension phase +1.

Study Day for the follow-up (FUD) phase will be calculated as date of visit/assessment – last dose date of study treatment (Date of EOT).

Fezolinetant Study Day (FD) will be calculated as date of visit/assessment – first dose date of fezolinetant +1. Note that this is the same as Study Day for subjects randomized to fezolinetant in the double-blind treatment phase. Post-baseline data prior to first dose of fezolinetant Day 1 is excluded from the analyses described in this SAP unless otherwise noted.

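### The 52-week SAP imputes incomplete AE onset dates from the first study-drug dose, so some on-fezolinetant events in placebo-switch subjects fall out of the TEAE tables

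*SAP*

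**What the plan says.** Three parts of the 52-week SAP set the start of the safety period at fezolinetant:

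- Section 6.5.1: "TEAE is defined as an AE observed after starting administration of fezolinetant and up to 21 days after the last dose of study drug".
- Section 5: "As a result, all endpoints in the 52-week analysis are from the first dose of fezolinetant and onward". The baseline table there puts the TEAE baseline of placebo/fezolinetant subjects at Week 12.
- Section 6.10.1: "Post-baseline data prior to first dose of fezolinetant Day 1 is excluded from the analyses described in this SAP unless otherwise noted".

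Protocol Section 7.9 uses imputed dates to allocate AEs to a treatment group, "in addition to determining whether an AE is/is not treatment emergent".

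Section 6.10.2 of the 52-week SAP then anchors incomplete onsets on the first study-drug dose: "If an onset date is missing, the imputed onset date will be the date of first dose of study drug". A year-only onset becomes the later of that dose and 1 January of the stated year. A month/year onset becomes the later of that dose and the first of the month, or simply the first of the month if that month precedes the dose. If the imputed onset falls after the AE end date, it is set to the end date. The 12-week SAP has the same text in its own Section 6.10.2.

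**The concern.** In the 12-week SAP the anchor and the TEAE start are the same date, so the rule is coherent. In the 52-week SAP the TEAE start has moved to fezolinetant and the imputation anchor has not. The two dates still coincide for subjects randomized to fezolinetant. For subjects switched from placebo they lie about 12 weeks apart.

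If study drug includes placebo, an event of uncertain onset in a switch subject can be dated to the placebo period and dropped from the 52-week TEAE tables, while the same event in a subject on fezolinetant from Day 1 is counted. The four groups are shown side by side, and the same TEAE status feeds the tables of serious events and of events leading to discontinuation. The error is anti-conservative. An affected event first reported during the extension could also miss the 12-week tables, which come from an earlier lock; Section 6.10 sends later findings about that period to an errata form.

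**Working it through.** **What study drug means here.** Usage in the 52-week SAP is mixed, so the texts have to be weighed.

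- Including placebo: the Key Terms start the double-blind period at the first administration of study drug. Section 6.5.5 uses the same anchor phrase: "Baseline biopsy will be defined as the non-missing value on or prior to first dose of study drug". The Section 5 table puts that biopsy baseline at initial randomization for placebo/fezolinetant subjects as well.
- Fezolinetant only: the Section 5 table row "Study drug exposure and compliance" uses Week 12 for switch subjects, and Section 6.3 measures compliance from first to last fezolinetant day.
- Where fezolinetant is meant as a start date, Sections 6.2.4, 6.5, 6.5.1 and 6.10.1 name it. Section 6.10.2 does not.

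The reading that includes placebo is the better one.

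**Which events are lost (switch subjects, rule as written).**

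- Fully missing: imputed to placebo Day 1, always lost.
- Year-only: lost whenever 1 January of the stated year precedes the switch.
- Month/year: lost only if the month is the switch month and the switch is not on the 1st.
- The end-date rule only moves an onset earlier, so it restores nothing.

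**Inputs for the size.** The plan gives no figure to reproduce. From the protocol's visit schedule: first fezolinetant dose at Day 85. Assumed: last dose Day 364 (52 × 7). TEAE window to Day 364 + 21 = 385, so 385 − 85 + 1 = 301 days on fezolinetant, against 84 on placebo. Onset uniform within each period. Randomization uniform from 1 July 2019 (A) or 30 September 2019 (B) to 30 March 2020; the protocol synopsis gives a Q3 2019 start, and 52-week SAP Appendix 1 gives the recruitment pause.

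**Method.** Each rule was applied to every combination of randomization date and true onset day. Share lost = on-fezolinetant onsets imputed before the switch ÷ all on-fezolinetant onsets. Share wrongly gained = placebo-period onsets imputed on or after the switch ÷ all placebo-period onsets. The amended rule is the one described under the fix, before its end-date rule.

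| Onset date known | Lost, current rule | Lost, amended rule | Gained, current rule | Gained, amended rule |
|---|---|---|---|---|
| Nothing | 100% | 0% | 0% | 100% |
| Year only | A 62.1%, B 83.9% | 0% | 0% | A 84.5%, B 76.8% |
| Month and year | A 4.9%, B 4.9% | 0% | 0% | A 17.5%, B 17.6% |

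The result depends on the calendar. Randomized 9 October 2019, switch 1 January 2020: year-only 0%, month/year 0%. Randomized one day later, switch 2 January: year-only 100%, month/year 30/301 = 10.0%.

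**Misplaced days per subject**, at a constant daily AE rate, current to amended: fully missing 301 to 84; year-only A 187.0 to 71.0, B 252.6 to 64.5; month/year A 14.7 to 14.7, B 14.6 to 14.8. The month/year shares agree: 14.7/301 = 4.9% and 14.7/84 = 17.5%.

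**End-date rule under the amended anchor.** With a known end date and an assumed exponential AE duration of median 7, 14 or 30 days, the shares gained fall to 11.4%, 23.1%, 43.6% (fully missing); A 11.0%, 21.5%, 38.9% and B 10.8%, 20.6%, 36.5% (year-only); A 7.6%, 11.0%, 13.9% and B 7.7%, 11.1%, 14.0% (month/year).

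**Number of events.** 150 × 0.8 = 120 switch subjects with 20% dropout, or 60 per group if split equally. Assume 60 to 180 AEs per group, with 0.5% to 5% incompletely dated: 60 × 0.005 = 0.3 to 180 × 0.05 = 9 such events. If all are month/year dates, about 0.3 × 0.05 = 0.015 to 9 × 0.05 = 0.45 are lost per group. If all are fully missing, 0.3 to 9 are lost. One subject in 60 is 1.7 percentage points.

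**The case against.** The anchor may not mean placebo Day 1. The Section 5 sentence that starts all 52-week endpoints at fezolinetant points to Section 6.10 for details, and 6.10.2 sits inside it. Section 6.2.4, like 6.3, seems to use study drug for fezolinetant when it defines concomitant medication. The biopsy baseline is a separately tabulated exception and says little about TEAEs. This shows that usage is mixed and that the reading is not certain. But nothing in 6.10.2 moves the AE anchor, and a rule that decides TEAE status should not depend on inference.

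The effect is small. No document gives a rate of incomplete onset dates. AEs are monitored continuously, and data should be entered within 5 days of a visit (protocol Table 1 footnotes and Section 8.1). Fully missing and year-only dates, which give the large percentages, should be rare. This stands.

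Re-anchoring gives no net accuracy for month/year dates: about 14.7 misplaced days either way. This also stands before the end-date rule; the gain there is one of direction. Finally, 6.10.2 has no imputation rule for AE end dates, so ongoing events or those without an end date get no relief from misattribution to fezolinetant. That is a fair limit on the reduced shares.

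**Conclusion.** The concern holds. On the better reading, 52-week SAP Section 6.10.2 contradicts the SAP's own TEAE definition for the two placebo-switch groups (up to 150 subjects, about 120 with 20% dropout) and removes some on-fezolinetant events of incomplete date. The shares lost are 100% (fully missing), about 62% to 84% (year-only) and about 5% (month/year, 0% to about 10% by start date). They rest on uniform accrual and onset and on the assumed accrual windows. Subjects on fezolinetant from Day 1, and month/year onsets after the switch month, are handled correctly.

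The likely number of events is small. The 52-week summaries are descriptive, so no hypothesis test and no randomized comparison is affected. The rule should still be corrected, because its error runs only off active drug and only in two of four groups shown together. Confidence is medium, because the meaning of study drug has to be inferred.

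**What to change.** In the AE onset rules of 52-week SAP Section 6.10.2:

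1. Make the first dose of fezolinetant the anchor, and keep the end-date rule.
2. For a year-only onset in a calendar year before the year of the first fezolinetant dose, keep the present rule so that the onset stays before fezolinetant. The month/year rule needs no extra clause.
3. Footnote every AE with a fully missing or partial onset date that was also counted as a placebo TEAE in the 12-week tables.

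This is one anchor term, one clause, one footnote and a programming parameter. The footnote also requires matching against the separately locked 12-week data. Results for subjects on fezolinetant from Day 1 do not change.

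The real cost is the reverse error: before the end-date rule, 100% of fully missing, about 77% to 84% of year-only and about 17.5% of month/year placebo-period onsets would count under fezolinetant. With a known end date and a median duration of 7 to 30 days, these fall to about 11–44%, 11–39% and 8–14%. That is the conservative direction for safety, and the footnote makes double counting visible.
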